6.3 Follow-up Visit	
7 ADVERSE EVENTS AND ADVERSE DEVICE EVENTS	12
7.1 Definitions	12
7.1.1 Adverse Event (AE)	12
7.1.2 Serious Adverse Event (SAE)	12
7.1.3 Anticipated Serious Adverse Device Effect (ASADE)	12
7.1.4 Unanticipated Serious Adverse Device Effect (USADE)	12
7.2 Recording AEs/ADEs and SAEs/SADEs	14
7.3 Follow-up of Subjects after AEs	14
8 POTENTIAL RISKS / BENEFITS	14
8.1 Potential Risks	14

Confidential and Proprietary

8.2 Potential Benefits	15
9 DATA ANALYSIS PLAN	16
9.1 Sample Size	16
9.2 Analysis Sets	16
9.3 Analysis of Exploratory/Efficacy Endpoints	16
9.4 Safety Analysis	16
10 STUDY MANAGEMENT AND ADMINISTRATIVE PROCEDURES	16
10.1 Training and Monitoring	16
10.2 Informed Consent	16
10.3 Protocol Compliance	17
10.3.1 Protocol Amendments	17
10.3.2 Protocol Deviations	17
10.4 Data Collection, Record Keeping and Storage	17
10.5 Subject Confidentiality	18
10.6 Publication Policy	18
REFERENCES	19
Appendix 1: Study Schedule	21
Appendix 2: Pain Rating Scale	22
Appendix 3: Before and After Treatment Instructions	23
Appendix 4: Subject Questionnaire	24
Appendix 5: Global Aesthetic Improvement Scale (GAIS)	26
Appendix 6: Investigator Evaluation	27

Protocol Summary

Title	Multi-Center Pilot Study of Cutera truSculpt Device
Objective	An exploratory pilot study to evaluate the safety, efficacy and ergonomics of Cutera truSculpt device
Study Design	Multi-center, exploratory pilot study
Enrollment	Approximately 60 subjects at multiple sites within the US
Safety Endpoint	Incidence and severity of adverse device events.
Exploratory Endpoints	
GAIS at 12 weeks post [REDACTED] final treatment from Baseline.
 
[REDACTED]
 
[REDACTED]
 
[REDACTED]
 
[REDACTED]
 
[REDACTED]
 
[REDACTED]
 
[REDACTED]
 
[REDACTED]

Subject Population	Female and male subjects between the ages of 18-65
Planned Schedule	First subject enrolled: May 2018 Last subject last visit: May 2019

1 PURPOSE

The purpose of this pilot study is to evaluate the truSculpt device.

2 BACKGROUND INFORMATION

Unwanted excess fat pockets/bulges have been among the top concerns expressed by patients in the aesthetic field. Although surgical interventions produce the most definitive results with body contouring, these invasive methods require significant recovery time and come with inherent risks.

[figure not shown]
[figure not shown]
As a non-invasive option, laser, intense pulsed light (IPL), RF, or a combination of these technologies have been developed to reduce cellulite and body circumference with minimal recovery time and risks [1]. The tightening effect of the thermal energy generated by these devices has been used for reduction in cellulite and body circumference in areas including but not limited to arms, abdomen, thigh, back and flanks [2-14]. Although lasers and IPLs can target the deep dermal layers, the thermal effects of these devices are limited due to light scattering and energy absorption by water in the dermis.

RF, which is the most studied device in the non-ablative category, uses electrical current rather than light energy. Unlike light energy, radio waves can penetrate deeper depending on the frequency of operation. RF can be used with all Fitzpatrick skin types without jeopardizing epidermal integrity [15].

Magnitude of thermal energy generated is dependent on the resistance (impedance) of the target tissue. When RF energy is conducted electrically to tissue, heat is produced as the tissue's inherent resistance (impedance) converts the electrical current to thermal energy [(J) = I x R x T where I = current, R = tissue impedance, and T = time of application)]. Subcutaneous fat which is a high impedance tissue generates greater heat and accounts for the deeper thermal effects of RF devices [15-18].

RF may be delivered in three different ways: 1) Monopolar when energy is applied as current between a single electrode tip and a grounding plate. 2) Bipolar when energy is applied between two points on the tip of a probe. 3) Unipolar when energy is delivered as the emission of electromagnetic radiation (EMR) rather than current and no grounding pad is necessary. This could be achieved by capacitive, inductive or resonant electrical coupling with the tissue.

3 STUDY OBJECTIVES

The objectives of this exploratory pilot study are to evaluate the safety, efficacy and ergonomics of the Cutera truSculpt RF device.

4 STUDY DESIGN

This is a multi-center, pilot study in approximately 60 subjects, ages 18 to 65. Subjects may receive [REDACTED] treatments and will be followed at 12 weeks post [REDACTED] final treatment.

4.1 Study Endpoints

4.1.1 Safety Endpoint

- Incidence and severity of adverse device events.

4.1.2 [REDACTED] Endpoints

- [REDACTED]
- [REDACTED].
- GAIS at 12 weeks post first and final treatment from Baseline.
- [REDACTED]
- [REDACTED]
- [REDACTED].

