4.2 Study Duration

Subjects enrolled in this trial will be asked to participate for approximately 3 months, depending on treatment(s).

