4.3.2 Safety Assessments

Following the first treatment, adverse events (AEs) will be assessed post-treatment and at each subsequent visit using the following scale:

1= mild: requires minimal or no treatment and does not interfere with the subject's daily activities.

2= moderate: may cause some interference with functioning.

3= severe: interrupts subject's usual daily activity and may require treatment.

Treatment-related Discomfort:

After each treatment, subjects will be asked to rate the average amount of discomfort experienced during treatment and immediately after treatment using the Pain Rating Scale (VAS Scale) Appendix 2.

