6 STUDY PROCEDURES

[REDACTED]

[REDACTED]

[REDACTED]

[REDACTED]

[REDACTED]

[REDACTED] y and informed consent
has been obtained, the subject will be enrolled in the study.
The first treatment may occur on the same day as the screening procedures.

[REDACTED]

[REDACTED]

[REDACTED]

[REDACTED]

[REDACTED]

[REDACTED]

[REDACTED]

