9.3 Analysis of Efficacy/Exploratory Endpoints

Formal hypothesis testing and statistical analysis are not planned for this study.

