10.6 Publication Policy

The investigator shall have the right to publish the results of the study. Unless mutually agreed upon in writing, prior to submission for publication of any manuscript, poster, presentation, abstract or other written or oral material describing the results of the study, the investigator shall allow sponsor to review manuscript, poster presentation, abstract or other written or oral material which describes the results of the study for the purpose only of determining if any patentable information is disclosed. At the sponsor's request, the investigator shall withhold any publication or presentation to permit sponsor to seek patent protection and to remove any confidential information from all publications.

[figure not shown]
A series of 12 horizontal black bars of varying lengths, decreasing in length from top to bottom. Each bar is preceded by a small white T-shaped notch on the left side.

A series of seven horizontal black bars of varying lengths, each with a small white rectangular notch at its left end. The bars are arranged vertically, with the first bar being the longest and the last bar being the shortest. The lengths of the bars decrease sequentially from top to bottom.

[figure not shown]
Confidential and Proprietary

Page 21 of 27
Version 1.0, 26APR2018

[figure not shown]
Confidential and Proprietary

Page 22 of 27
Version 1.0, 26APR2018

Confidential and Proprietary

Page 24 of 27
Version 1.0, 26APR2018

Confidential and Proprietary

Page 25 of 27
Version 1.0, 26APR2018

Appendix 5

Week 12-Investigator Global Aesthetic Improvement Scale (GAIS): Compared to Baseline Photos

0	No Change
+1	Mild Improvement
+2	Moderate Improvement
+3	Significant Improvement

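### Do the two 12-week GAIS time points conflict with a participation of about 3 months?

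*Protocol*

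**What the plan says.** Section 4.1.2 of the protocol sets the aesthetic endpoint as "GAIS at 12 weeks post first and final treatment from Baseline". Section 4.2 states: "Subjects enrolled in this trial will be asked to participate for approximately 3 months, depending on treatment(s" (the closing bracket of the last word is cut off here). The clause after the comma is part of the statement and makes the figure conditional.

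Section 4 gives the number of sessions only as a blacked-out figure, followed by "treatments and will be followed at 12 weeks post". More than one session is clearly possible, because section 4.3.2 provides that "After each treatment, subjects will be asked to rate the average amount of discomfort experienced during treatment". Section 6 adds that "The first treatment may occur on the same day as the screening procedures", so screening need not lengthen participation. The rest of section 6 is largely redacted, and the Appendix 1 schedule is not shown.

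The Protocol Summary gives the calendar: "First subject enrolled: May 2018 Last subject last visit: May 2019". The visible form in Appendix 5 is headed "Week 12-Investigator Global Aesthetic Improvement Scale (GAIS): Compared to Baseline Photos". Section 9.3 says of the analysis: "Formal hypothesis testing and statistical analysis are not planned for this study".

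**The concern.** Naming both a first and a final treatment matters only if the two differ for some subjects. For such a subject, participation lasts 12 weeks plus the time from first to final treatment. If the next session comes before week 12, the post-first rating already reflects it. If it comes at week 12 or later, the subject stays at least 24 weeks, well beyond 3 months. On that reading one of the two sections must give way, whatever the redacted interval is.

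Two things would be at stake. A reader might take the two ratings as the effect of one session and of the full course, and neither could then be attributed to a number of sessions. An understated duration would also bear on commitments in section 5.1.1 that last as long as the study does: smoking, weight, other procedures and contraception. The Appendix 5 heading, which counts to week 12 without naming the treatment it counts from, adds to the impression of an unsettled schedule.

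**Working it through.** **Inputs.** The follow-up of 12 weeks after the final treatment comes from sections 4 and 4.1.2. The stated participation comes from section 4.2. Same-day start is permitted by section 6, so screening time is taken as zero. The gap g between first and final treatment is not visible, so the values below are assumptions.

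**Formulas.** Participation in weeks = 12 + g. One month = 365.25 / 12 / 7 = 4.348 weeks, so participation in months = (12 + g) / 4.348. When g is under 12, the post-first rating falls 12 − g weeks after the final treatment.

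**The plan's own figure.** For a single treatment g = 0, and 12 / 4.348 = 2.76 months. Three months is 3 × 4.348 = 13.0 weeks. The stated figure is reproduced.

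**Range over assumed gaps.**

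| g (weeks) | Participation (weeks) | Months | Position of post-first rating |
|---|---|---|---|
| 0 | 12 | 2.76 | same as post-final rating |
| 1 | 13 | 2.99 | 11 weeks after final treatment |
| 2 | 14 | 3.22 | 10 weeks after final treatment |
| 4 | 16 | 3.68 | 8 weeks after final treatment |
| 8 | 20 | 4.60 | 4 weeks after final treatment |
| 12 | 24 | 5.52 | at the time of the final treatment |
| 16 | 28 | 6.44 | 4 weeks before final treatment |

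**What the table shows.**

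1. The 3-month figure is not confined to subjects whose first and final treatment almost coincide. A 1-week gap (2.99 months) fits better than no gap at all (2.76 months), and a 2-week gap (3.22 months) still fits.
2. For a retreated subject, a flat 3 months and a post-first rating free of later sessions are indeed incompatible. The clean rating needs a gap of at least 12 weeks from the first session to the next, hence at least 24 weeks in the study. That is 5.52 / 3 = 1.8 times the stated figure.
3. Section 4.2 does not state a flat 3 months. With its conditional clause, 3 months can describe the single-treatment or short-course subject, and a longer stay can apply to others. Retreatment after the first 12-week rating then satisfies sections 4.1.2 and 4.2 together, with neither defect.
4. The calendar permits this. May 2018 to May 2019 is about 52 weeks. A 24-week participation leaves about 52 − 24 = 28 weeks for enrolment, and a 12-week participation leaves about 40.

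**The other strands.**

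- *Attribution.* Section 4.1.2 defines two time points against baseline. No visible text says that the first of them measures the effect of one session. A rating that follows a later session is a mixture only relative to that unstated purpose.
- *Pooling.* Nothing visible says that subjects with different numbers of sessions will be summarised together. Such tabulations are commonly left to the statistical analysis plan, which is not at hand.
- *Redacted wording elsewhere.* The Protocol Summary and sections 4 and 4.3.1 have a blacked-out gap just before the reference to the final or last treatment, where section 4.1.2 also names the first. That is no evidence of a different time point.
- *Appendix 5.* Most of the other appendix pages are not shown. The visible form cannot be assumed to be the only one, and the unseen schedule may define its week 12.
- *Commitments.* Those in section 5.1.1 run for the study's own length and none is tied to 3 months. They extend with actual participation.

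**The case for a change.** The strongest case for the concern is that its core does not need the redacted interval. The text names two anchors, foresees repeat sessions and gives one duration figure. For any gap, a retreated subject has either a post-first rating taken after a later session or a stay of at least 24 weeks. The conditional clause rescues the duration only by leaving it open: it supplies no maximum, so section 4.2 alone does not say whether a retreated subject stays 3 months or nearer 6. The absence of formal testing does not settle the matter either, because in a purely descriptive study the meaning of a rating rests on when it is taken.

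The arithmetic stands, and so does the remark on testing: section 9.3 does not by itself dispose of the concern. It is also true that the visible text gives no upper duration and does not say whether the post-first rating precedes any further session. But these are points not visible, not points stated wrongly. The visit procedures and the schedule, where such details would be found, are blacked out or not shown, and missing text of that kind cannot be counted against the plan. The claim that the two sections cannot both hold fails once the conditional clause is read with them.

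**Conclusion.** The concern does not hold. Section 4.2 is accurate for a single treatment (2.8 months) and for gaps of 1 to 2 weeks (3.0 to 3.2 months), and its wording allows longer participation for other subjects. A further session after the first 12-week rating, with at least 24 weeks (5.5 months) in the study, would fit the endpoint, the duration statement and the study calendar at once.

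The longer durations in the table rest on assumed gaps, since the real spacing is not visible. It is therefore unknown whether any subject's post-first rating follows a later session, and a statement that all retreated subjects are affected only repeats the assumption of a gap under 12 weeks. The conclusion rests on reading the conditional clause in section 4.2 as letting participation vary with the treatments received, which is its ordinary meaning. What is left is a possible request for a stated maximum, the visit order, a form label and a table by number of sessions. The redacted schedule or the statistical analysis plan may already settle these, and none of them is an error in the protocol.

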4.2 Study Duration

Subjects enrolled in this trial will be asked to participate for approximately 3 months, depending on treatment(s).

4.3 Study Assessments

4.3.1 Exploratory Assessments

Subjects will undergo circumferential measurement 12 weeks post [REDACTED] final treatment visit. The difference in measurement from baseline and at 12 weeks post [REDACTED] last treatment will be calculated and reported.

An assessment of the device along with the Global Aesthetic Improvement of the subjects from baseline vs. 12 weeks post [REDACTED] last treatment.

[REDACTED]

[REDACTED]

[REDACTED]

4.3.2 Safety Assessments

Following the first treatment, adverse events (AEs) will be assessed post-treatment and at each subsequent visit using the following scale:

1= mild: requires minimal or no treatment and does not interfere with the subject's daily activities.

2= moderate: may cause some interference with functioning.

3= severe: interrupts subject's usual daily activity and may require treatment.

Treatment-related Discomfort:

After each treatment, subjects will be asked to rate the average amount of discomfort experienced during treatment and immediately after treatment using the Pain Rating Scale (VAS Scale) Appendix 2.

4.4 Study Discontinuation

Cutera, Inc. (the sponsor) has the right to terminate this study at any time. Reasons for terminating the study may include, but are not limited to, the following: incidence or severity of adverse events in this or other studies indicates a potential health hazard to subjects; subject enrollment is unsatisfactory; number of protocol deviations is unacceptable; data recording is inaccurate or incomplete; or questionable study site compliance with ICH-E6, Good Clinical Practice.

4.5 Investigator Selection

The Investigator(s) will be invited to participate in the study based on his or her medical specialty, experience conducting clinical research studies and experience in the use of RF devices for aesthetic indications. Access to potential study subjects and the Investigator's sincere interest in this study along with expressed willingness to cooperate with the study process and requirements are also considered.

5 STUDY POPULATION

5.1 Study Subject Recruitment and Selection

Approximately 60 male or female subjects, ages 18 to 65, who desire treatment with truSculpt. Subjects will be recruited to participate from the local population. Subjects may also be recruited from the Investigator's existing patient database or from patients who present themselves to the study site requesting treatment. Only subjects who meet all eligibility criteria and who provide written informed consent will be enrolled into the study.

Each subject will be evaluated by the Investigator to assess his/her suitability for entry into the study according to the following inclusion and exclusion criteria.

5.1.1 Inclusion Criteria

To be included in the study, subjects must meet all of the following Inclusion Criteria:

1. Subject must be able to read, understand and sign the Informed Consent Form.
2. Female or Male, 18 to 65 years of age (inclusive).
3. Subject has visible fat bulges in the area to be treated.
4. Non-smoking for at least 6 months and willing to refrain from smoking for the duration of the study.
5. Subject must agree to not undergo any other procedure(s) in the treatment region during the study period.
6. Subject must adhere to the follow-up schedule and study instructions.
7. Subject must adhere to the same diet and/or exercise routine throughout the study, and agree to maintain the same weight throughout the study.
8. Willing to have photographs taken of the treatment area and agree to use of photographs for presentation, (educational and/or marketing), publications, and any additional marketing purposes.
9. For female subjects: not pregnant or lactating and is either post-menopausal, surgically sterilized, or using a medically acceptable form of birth control prior to enrollment and during the entire course of the study.

5.1.2 Exclusion Criteria

Subjects will be excluded from the study if they meet any of the following Exclusion Criteria:

1.	Participation in a clinical trial of another device or drug within 1 month of study participation, or during the study period.
2.	Any type of prior cosmetic treatment to the target area within 6 months of study participation.
3.	Any prior invasive cosmetic surgery to the target area, such as liposuction.
4.	Has a pacemaker, internal defibrillator, implantable cardioverter-defibrillator, nerve stimulator implant, cochlear implant or any other electronically, magnetically or mechanically activated implant.
5.	Has metal implant(s) within the body, such as artificial heart valves.

6.	Significant uncontrolled concurrent illness that in the opinion of the Investigator would make the subject unsuitable for inclusion.
7.	History of any disease or condition that could impair wound healing.
8.	History of keloid formation, hypertrophic scarring or abnormal/delayed wound healing.
9.	Skin abnormality in the treatment area that in the opinion of the Investigator would make the subject unsuitable for inclusion.
10.	Currently undergoing systemic chemotherapy or radiation treatment for cancer, or history of treatment in the target area within 3 months of study participation.
11.	Allergy or sensitivity to Tegaderm.
12.	As per the Investigator's discretion, any physical or mental condition which might make it unsafe for the subject to participate in this study or a condition that would compromise the subject's ability to comply with the study requirements.

5.2 Subject Numbering

If a subject completes the Informed Consent Form, meets the study eligibility criteria and is willing to participate, the subject will be assigned a study subject identification number. This number is comprised of a site number (which is provided by the sponsor) and a sequential subject number and the subject initials (first and last names).

5.2.1 Subject Discontinuation Criteria

If possible, every subject should remain in the study until completion of the required follow-up period. However, participation in this study is completely voluntary and a subject can choose to withdraw from the study at any time. Decision to withdraw will not affect or prejudice the subject's continued medical care in any way. In those instances, the investigator will attempt to obtain a final clinical assessment and an adverse device effect evaluation for the subject prior to this withdrawal. A subject will be considered lost to follow-up only after three unsuccessful, documented attempts to contact the subject have been made.

In addition, a subject can be discontinued for any of the following reasons: the Principal Investigator decides that continuing in the study would not be in the subject's best interest, a subject is noncompliant with the protocol, a subject has a serious reaction to the treatment, a subject develops any of the exclusion criteria during the study period or the study is stopped by the study sponsor.

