7.3 Follow-up of Subjects after AEs

All reported AEs/ADEs/SAEs/SADEs should be followed until resolution or until the subject's participation in the study ends. Resolutions of AEs/ADEs/SAEs/SADEs are to be documented on the appropriate CRFs. All ADEs that result in permanent discontinuation from this clinical trial, whether serious or not, should also be reported on the subject Non-Completion of Study Form.

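### Protocol 5.2.1 does not separate stopping treatment from leaving the study, so 12-week efficacy data may be lost for reasons that could relate to outcome

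*Protocol*

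**What the plan says.** Protocol 5.2.1 opens with a retention default: "If possible, every subject should remain in the study until completion of the required follow-up period". It then covers voluntary withdrawal and asks the investigator to attempt a final clinical assessment and an adverse device effect evaluation before the subject leaves. A second list follows: "In addition, a subject can be discontinued for any of the following reasons". The reasons include that "the Principal Investigator decides that continuing in the study would not be in the subject's best interest", that "a subject is noncompliant with the protocol, a subject has a serious reaction to the treatment, a subject develops any of the exclusion criteria", and that the sponsor stops the study.

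The wording throughout concerns the study, not the treatment. Section 7.3 is consistent with this: "All ADEs that result in permanent discontinuation from this clinical trial, whether serious or not, should also be reported" on the non-completion form. Section 7.3 also has adverse events followed until they resolve or the subject's participation ends.

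Two entry rules matter here. Exclusion criterion 9 (5.1.2) is "Skin abnormality in the treatment area that in the opinion of the Investigator would make the subject unsuitable for inclusion". Inclusion criterion 7 (5.1.1) reads "Subject must adhere to the same diet and/or exercise routine throughout the study, and agree to maintain the same weight throughout the study".

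Efficacy is read at 12 weeks. Section 4.1.2 lists GAIS at that time against baseline, and section 4.3.1 says of circumference: "The difference in measurement from baseline and at 12 weeks post [REDACTED] last treatment will be calculated and reported". Section 9.2 limits the analysis sets to enrolled subjects who complete treatment, and section 9.3 plans no formal testing.

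**The concern.** Entry criteria decide who should be exposed. After exposure, a breach may be a reason to give no further treatment, but it is not in itself a reason to stop measuring. The visible text of 5.2.1 has no status for a subject who stops treatment and stays in follow-up, so using any of these grounds also ends measurement.

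Some of the grounds could be connected with the result. A skin abnormality in the treated area could affect a GAIS rating, and a change in weight bears directly on circumference. The site makes these decisions, possibly during the 12-week wait and with the subject in view.

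Efficacy is a stated objective (section 3), and the visible text describes no comparison group. The descriptive 12-week summary is therefore the efficacy result, and the absence of a formal test does not protect it from selective loss. A subject removed after completing treatment belongs to the 9.2 set but has no 12-week value. A subject removed between treatments falls outside the set altogether. Removal after a serious reaction could also cut short the follow-up of that reaction under 7.3.

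**Working it through.** **Step 1: what the text provides for each route out.**

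- Voluntary withdrawal: a final assessment is attempted. It takes place at exit and is not the 12-week measurement.
- Investigator-initiated exit for noncompliance, a serious reaction or a new exclusion criterion: these come in a later, additional list. The final-assessment sentence refers back to voluntary withdrawal, so no assessment step is visible for them.
- Stopping treatment but staying in follow-up: not mentioned in the visible text.

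**Step 2: the plan's own figure.** Section 9.1 gives 60 subjects as a judgement, with no effect size, standard deviation, precision target or dropout rate. There is nothing to reproduce, and no expected number of discontinuations to use.

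**Step 3: bounds on an improvement rate.** From the document: N = 60. Assumed: all 60 are treated, k of them are removed before week 12, and r of the remaining 60 − k have improved.

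- Observed rate = r/(60 − k)
- Full-cohort rate if no removed subject would have improved = r/60
- Full-cohort rate if every removed subject would have improved = (r + k)/60

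With an observed rate of about 70% (assumed):

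| k | Observed | None of the removed improve | Overstated by (points) | All of the removed improve | Understated by (points) |
|---|---|---|---|---|---|
| 1 | 41/59 = 69.5% | 41/60 = 68.3% | 1.2 | 42/60 = 70.0% | 0.5 |
| 3 | 40/57 = 70.2% | 40/60 = 66.7% | 3.5 | 43/60 = 71.7% | 1.5 |
| 6 | 38/54 = 70.4% | 38/60 = 63.3% | 7.0 | 44/60 = 73.3% | 3.0 |
| 12 | 34/48 = 70.8% | 34/60 = 56.7% | 14.2 | 46/60 = 76.7% | 5.8 |

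For observed rates from about 50% to 90% and k from 1 to 12:

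- Smallest worst-case overstatement: 30/59 − 30/60 = 50.8% − 50.0% = 0.8 points.
- Largest worst-case overstatement: 43/48 − 43/60 = 89.6% − 71.7% = 17.9 points.
- Largest understatement: 36/60 − 24/48 = 60.0% − 50.0% = 10.0 points.

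If removed subjects improve at the same rate as those who stay, the bias is zero for any k.

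**Step 4: circumference.** Observed mean change minus full-cohort mean change equals (k/60) × (mean of those who stay − mean of those removed). The document gives no circumference values, so this cannot be put in centimetres. Its sign depends on who is removed: losing subjects who gained weight makes the reduction look larger, and losing subjects who lost weight makes it look smaller.

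**The case against.** A reader might infer that 5.2.1 ends participation for these subjects, and that the missing 12-week values would fall mainly on those doing badly. The documents do not support that reading.

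- **The rule is permissive.** It says a subject can be discontinued, under a default that subjects stay to the end of follow-up if possible.
- **The link to outcome is partial.** Joining another trial, a new implant, chemotherapy or a Tegaderm allergy has no evident connection with GAIS or circumference. Inclusion criterion 7 is breached as much by a subject who diets and loses weight as by one who gains it.
- **The outcome-related examples need interpretation.** Criterion 9 depends on the investigator's view of suitability for entry, and criterion 8 on scarring and healing is worded as history. Criterion 7 asks for agreement to maintain weight, with no visible threshold for a breach.
- **Redaction limits the claim.** Section 6, including the follow-up visit, is almost wholly blacked out and the schedule is not shown. Section 7.3 mentions a non-completion form, so some exit process exists.
- **The upper bounds are extreme.** They need every removed subject to be a non-improver. With a true rate of 36/60 = 60%, if 6 are removed and 3 of them had improved, the observed rate is 33/54 = 61%.

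All of these points stand, and they limit the claim without removing it. Discretion does not prevent selective loss, because it allows the decision to depend on how the subject looks. Nor does a permissive rule create a treatment-only status that the visible text lacks.

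**Conclusion.** The point holds as a weakness in what 5.2.1 permits. The visible text does not distinguish stopping treatment from leaving the study. It allows investigator-initiated exit after treatment on grounds that may relate to outcome, and it requires no 12-week assessment for those subjects. The descriptive 12-week GAIS and circumference results may be biased as a result.

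Neither direction nor size is known from the document. On assumed losses of 1 to 12 of 60, overstatement of the improvement rate could be anywhere from zero to a worst case of about 1 to 18 points, and understatement is also possible. The conclusion rests on the visible text alone, and a redacted early-exit procedure could already close part of the gap. Since no formal test is planned, what is at stake is the accuracy of descriptive summaries in a pilot study. The change is still worth making, because a 12-week value that was never collected cannot be recovered at analysis.

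**What to change.** In 5.2.1, state that noncompliance, a serious reaction or a newly developed exclusion criterion does not by itself end data collection. Any subject who has had at least one treatment is asked to attend the planned 12-week circumference, photograph and GAIS assessment and to continue adverse event follow-up. The exceptions are that the subject withdraws consent, the investigator judges continued participation not to be in the subject's best interest, or the sponsor stops the study. Record the event as a protocol deviation where it is one, and report the number and reasons with the results.

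Align 9.2 so that treated subjects with 12-week data who did not complete treatment are also summarised. Without this, the added data would still be left out for anyone stopped between treatments. Check the wording against the redacted section 6 and the schedule. Leave the grounds for stopping treatment unchanged.

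The cost is a paragraph in 5.2.1 and a sentence in 9.2. The 12-week assessment is already part of the plan. The downside is that the results will include noncompliant subjects and may look slightly less favourable.
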